2.9 Randomisation

Eligible individuals who have provided and consent will be allocated to tecovirimat or placebo using a minimised randomisation program that helps maximise balance between the allocated treatment groups with respect to the following prognostic variables:

- Age (<18, ≥18-<40, ≥40)
- Sex at birth (male/female)
- Previous orthopoxvirus vaccination (yes/no/not known)
- Severity of rash (localised vs disseminated, defined as >1 body area affected)
- Days since onset of rash (≤7 days or >7 days)

The implementation of the randomisation procedure will be monitored by the Senior Trials Programmer, and the Trial Steering Committee notified if an error in the randomisation process is identified.

2.10 Blinding

PLATINUM is a placebo-controlled trial in order to avoid knowledge about the treatment allocation impacting (or being perceived to impact) the assessment of clinical outcomes and adverse events or adherence to the study procedures (e.g. completion of questionnaires or collection of samples). While the study is in progress, access to the treatment allocation for individual participants and tabular results of study outcomes by allocated treatment allocation will not be available to anyone other than the Data Monitoring Committee (DMC) and the statistical team responsible for preparing analyses for the DMC.

2.11 Data collection schedule

Baseline information will be entered into a web-based electronic case-report form (eCRF) by the CCO staff at the time of randomisation (day 0). Follow-up information will be collected using a daily eCRF completed by the participant on days 1-28, and a weekly eCRF completed by CCO staff during remote review on days 7, 14, 21 and 28. Participants will also be asked to self-collect swabs from their throat and most recent active skin or mucosal lesion at days 7, 14, 21, and 28 (each ±2 days). The same information will be collected from all study participants if possible, irrespective of whether they start or complete the scheduled course of allocated study treatment.

All randomised participants are to be followed up for 28 days after randomisation. Longer term (up to 1 year) follow-up may be sought through linkage to electronic healthcare records and medical databases including those held by NHS Digital, the UK Health Security Agency and equivalent bodies. Additional follow-up calls may be conducted following the end of the main assessment period of the study (28 days) to assess complete resolution of monkeypox symptoms and other relevant adverse events.

2.12 Data monitoring

During the study, interim analyses of unblinded study data (including information on the pre-specified primary, secondary and safety outcomes) will be supplied in strict confidence to the independent DMC. The DMC will request such analyses at a frequency relevant to the stage of the study and the speed and volume of new information (typically every 6 months with a Chair's review at 3 months) or in response to emerging information from other studies.

The DMC will independently evaluate these analyses and any other information considered relevant. The DMC will review the analyses among children (age <18 years) both separately and combined with the adult data. The DMC is expected to advise the Chief Investigator and Chair of the Trial Steering Committee if, in the view of the DMC, there is compelling evidence of *hazard* that seems likely to outweigh any potential benefit (either overall or in a particular subgroup of participants).

A single interim assessment for *benefit* is to take place when 50% of the originally planned number of participants have reached determination of the primary endpoint (i.e. experienced active lesion resolution before or at day 28 or reached 28 days of follow-up). A group sequential design was used to generate asymmetric two-sided boundaries based on Hwang-Shih-DeCani alpha and beta spending functions for efficacy and non-binding futility assessments (Table 2).⁴

Table 2. DMC guidance for interim analysis of benefit

		Lower bounds (futility assessment)		Upper bounds (efficacy assessment)	
Analysis	N	Z-statistic	P-value*	Z-statistic	P-value*
Interim	216	0.42	0.6616	2.75	0.0030
Final	432	1.98	0.9762	1.98	0.0238

*One-sided p-values; the one-sided p-value of the final analysis of 0.0238 corresponds to a two-sided p-value of 0.0476. Boundaries estimated using R package gsDesign

The DMC will assess the effect of tecovirimat vs. placebo on the primary outcome against these criteria and advise the Chief Investigator accordingly. In considering its recommendations, the DMC should also take account of the totality of the evidence from the trial data (including effects on secondary and other outcomes and in key participant subgroups) and any other information from external sources that it considers relevant (e.g. results from other trials, emerging information on the nature of the disease and its epidemiology).

The Chief Investigator is responsible for considering the advice of the DMC in discussion with members of the Trial Steering Committee, amending the protocol accordingly, and making the information available to the public. Unless this happens, the Trial Steering Committee, Chief Investigator, study staff, investigators, study participants, funders and other partners will remain blind to the treatment allocation for individual participants and to the interim results until 28 days after the last patient has been randomised (at which point unblinded analyses may be conducted).

Further details about the role and membership of the independent Data Monitoring Committee are provided in the protocol.

2.13 Trial reporting

The trial will be reported according to the principles of the CONSORT statement.⁵

2.14 Analysis population

The intention to treat (ITT) population will be all participants randomised, irrespective of treatment received. This ITT population will be used for analysis of efficacy and safety data. For interim analyses, baseline data will be reported for all participants with data available and outcome data will be reported for all participants who have reached day 28 after randomisation.

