2.9 Central assessment of SAEs and onward reporting of SUSARs

All serious adverse events (SAEs) will be documented and their causal relationship to the study treatment will be assessed by the Chief Investigator or designee. Serious Adverse Events that are believed with a reasonable probability to be due to the study treatment will be considered a Suspected Serious Adverse Reaction (SSAR) (https://database.ich.org/sites/default/files/E2A_Guideline.pdf).

Clinicians at the Central Coordinating Office are responsible for expedited review of reports of SSARs received. Additional information (including relevant medical and medication history) will be sought from relevant healthcare teams. An assessment made of whether the event is “expected” or not (assessed against the relevant Reference Safety Information*). Any SSARs that are not expected would be considered a Suspected Unexpected Serious Adverse Reaction (SUSAR).

All confirmed SUSARs will be reported to the Chair of the DMC, the trial sponsor, and to MHRA and the ethics committee, in an expedited manner in accordance with regulatory requirements.

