2.6 Outcomes

2.6.1 *Primary outcome*

Time (in days) to active lesion resolution, defined as the first day on which all skin lesions are scabbed or desquamated (and mucosal lesions healed), up to 28 days after randomisation.

2.6.2 *Secondary clinical outcomes*

- (i) Time (in days) to complete lesion resolution, defined as the first day on which all lesions are completely resolved (all scabs dropped off and intact skin remains underneath, and mucosal lesions healed), up to 28 days after randomisation
- (ii) Time to negative throat swab viral culture, defined as time to consistently negative culture for monkeypox virus on throat swab at Days 7, 14, 21, and 28
- (iii) Time to negative skin or mucosa swab viral culture, defined as time to consistently negative culture for monkeypox virus on swab of most recent active skin or mucosa lesion at Days 7, 14, 21, and 28

2.6.3 *Subsidiary clinical outcomes*

- (i) Clinical status on day 7, 14, 21 and 28 according to the following ordinal scale:
 - a. All lesions completely resolved (all scabs dropped off and intact skin remains underneath, and all mucosal lesions healed)
 - b. Active lesions resolved (all skin lesions scabbed or desquamated, but not all completely resolved)
 - c. Active lesions persist but no new lesions in last 24 hours
 - d. New active lesion(s) in last 24 hours.
- (ii) Throat swab monkeypox DNA levels: monkeypox virus DNA concentration in throat swabs at Days 7, 14, 21, 28
- (iii) Number (%) of patients admitted to hospital for a complication of monkeypox (overall and by type)
- (iv) Time to sustained absence of use of analgesia for monkeypox symptoms, defined as time to consistently reporting no use of analgesia, up to 28 days after randomisation.

2.6.4 *Safety assessments*

- (i) Number (%) of patients suffering serious adverse events (overall and by type) within 28 days of randomisation
- (ii) Number (%) of patients suffering adverse events of special interest (overall and by type) within 28 days of randomisation. These are:
 - Vomiting
 - Diarrhoea
 - Fever
 - Severe tiredness
 - Swollen lymph glands
 - Headache

- Muscle or joint pain
 - Sore eyes
 - Shortness of breath
 - Secondary skin infection
 - Pain related to monkeypox symptoms
- (iii) Number (%) of patients suffering death, overall and by cause
- (iv) Reasons for prematurely stopping allocated study treatment

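### SAP 2.14 leaves safety events in participants before day 28 out of the DMC's interim by-arm tables, a limit that protocol 2.10 does not set

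*SAP*

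**What the plan says.** SAP 2.14 first defines the intention-to-treat population as everyone randomised and adds: "This ITT population will be used for analysis of efficacy and safety data". It then sets two denominators for interim reports. The first is broad: "For interim analyses, baseline data will be reported for all participants with data available". The second is narrower: "outcome data will be reported for all participants who have reached day 28 after randomisation". No exception is made for safety.

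The SAP treats safety as outcome data. Its section 2.6, Outcomes, contains 2.6.4, which lists "Number (%) of patients suffering serious adverse events (overall and by type) within 28 days of randomisation", adverse events of special interest, "Number (%) of patients suffering death, overall and by cause", and reasons for stopping treatment early. Section 4.1.4 is headed Safety outcomes. SAP 2.12 describes the interim analyses of unblinded data as "including information on the pre-specified primary, secondary and safety outcomes) will be supplied in strict confidence to the independent DMC", and gives their frequency as "typically every 6 months with a Chair's review at 3 months".

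Protocol 2.10 gives the DMC the same content at the same frequency and the same task of advising on hazard, but has no restriction by day of follow-up. Outside the interim reports, protocol 2.9 provides one expedited route: "All confirmed SUSARs will be reported to the Chair of the DMC". It carries no condition on the participant's day of follow-up.

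**The concern.** Study drug is taken on days 1-14 (protocol section 3 flowchart) and safety is collected to day 28 (protocol 2.8). Under the SAP 2.14 rule, a participant now on treatment, or in the two weeks after it, appears in the DMC's baseline table but contributes no event to its outcome tables.

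This matters because, apart from the statisticians who prepare its reports, only the DMC sees results by arm (protocol 2.11, SAP 2.10). An imbalance in events that were each judged unrelated or expected can be seen only in a comparison by arm. The trial also admits immunocompromised patients and children, in whom the protocol says safety has not been established and no clinical trials have been done (protocol 2.2.2 and 2.2.4).

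The point is about interim safety reporting only. It does not touch the boundaries or size of the single look for benefit, or the final analysis.

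**Working it through.** **Step 1: does the restriction cover safety?** Three places in the SAP class safety as outcomes: 2.6.4 (within 2.6, Outcomes), 2.12 and 4.1.4. The only other category in the interim sentence of 2.14 is baseline data, which is given to the DMC for everyone. So the day-28 condition, as written, applies to safety. Protocol 2.10 has no matching condition, so the SAP is the narrower of the two.

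**Step 2: which events are affected, and which still get through?**

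| Event before day 28 | Stated route to the DMC at that time |
|---|---|
| Confirmed SUSAR, fatal or not | Expedited to the DMC Chair (protocol 2.9) |
| Serious reaction judged expected | None stated |
| SAE or death judged unrelated | None stated |
| Adverse event of special interest | None stated |
| Treatment stop | None stated |

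**Step 3: how long is the delay?** An event on day *d* becomes eligible for the tables after 28 − *d* days. For day 3 that is 25 days, and for day 14 it is 14 days. The event is seen only at the next report after that. With a report typically every 6 months and a Chair's review at 3 months, an event that misses one cut-off may wait about 3 to 6 months.

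**Step 4: early deaths and withdrawals.** The SAP does not define reaching day 28 for someone whose follow-up ends sooner. If it means that 28 calendar days have passed since randomisation, the person enters the tables late. If it means being followed to day 28, the person never enters the interim tables.

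**Step 5: how many people?** The plan gives no figure for this and no recruitment rate. It gives only the target of 500 (protocol 2.6, SAP 2.8). I assume uniform accrual and a month of 30.4375 days.

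Share of randomised participants left out at a look *t* days after the start = 28 / *t*. Share in the 14-day treatment period = 14 / *t*.

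- At 3 months (*t* = 91.3): 28/91.3 = 31% left out; 14/91.3 = 15% on drug.
- At 6 months (*t* = 182.6): 28/182.6 = 15% left out; 14/182.6 = 8% on drug.

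These shares do not depend on the recruitment rate. The number of people does: it is 28 × 500 / (recruitment period in days), for any cut-off while recruitment continues.

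| Assumed recruitment period | Randomised per day | Left out (28 days) | Of whom on drug (14 days) |
|---|---|---|---|
| 6 months | 2.74 | 77 | 38 |
| 12 months | 1.37 | 38 | 19 |
| 18 months | 0.91 | 26 | 13 |
| 24 months | 0.68 | 19 | 10 |

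**The case against.** A reader might infer that the DMC looks for hazard with no serious event at all from people on study drug. The documents do not support that. Confirmed SUSARs, fatal ones included, reach the DMC Chair whatever the day of follow-up. Protocol 2.10 and SAP 2.12 also let the DMC set the frequency of analyses and weigh other relevant information. Nor are most events lost, since they enter the tables after day 28.

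Other arguments on that side:

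- **The sentence does not say that only these participants are reported.** True, but the contrast with baseline data makes the restrictive reading the natural one.
- **SAP section 1 describes the document's scope as the main paper, and a DMC Charter (protocol 2.10) may settle the contents of the reports.** The Charter is not among the documents, so what the DMC actually receives cannot be known from them. SAP 2.14 nevertheless states an interim rule, and a report team following it would leave these data out.
- **There is other oversight before day 28.** Potential SAEs go to the Chief Investigator or designee within 24 hours (protocol 2.8). Coordinating-office medical staff review all adverse events and reasons for stopping (protocol summary). Allocation may be unblinded when a suspected serious reaction is reviewed (protocol 2.11). This stands as case-by-case oversight, but none of it gives a comparison by arm.
- **Many people on a 14-day course would finish before DMC advice took effect, and review frequency drives most of the delay.** This is fair and limits the benefit for those on drug at a cut-off. With 6-month recruitment, the 6-month look would also fall as enrolment ends. Later participants in a slower trial would still gain from an earlier signal.
- **Completed follow-up is a coherent denominator for a percentage within 28 days.** It is, and it can be kept beside a table of all events to the cut-off.

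**Conclusion.** The point holds as an avoidable gap in interim safety reporting. SAP 2.14, as written, keeps SAEs, deaths, special-interest events and treatment stops in participants before day 28 out of the by-arm tables, although protocol 2.10 sets no such limit. For most events other than SUSARs the effect is a delay: up to 28 days in eligibility, and in practice until the next report. For early deaths and withdrawals the wording leaves open permanent omission from interim tables.

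The size rests on assumed uniform accrual: about 31% of randomised participants left out at 3 months and 15% at 6 months, about half of them on drug. A reader might settle on 77 people as the size of the gap, but that is only the 6-month recruitment case. The documents give no recruitment rate, and 24 months would give about 19.

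This should be fixed because it is cheap and bears on participant protection during the trial. It does not affect the final efficacy or safety results, or error control.

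**What to change.** In SAP 2.14, split the interim sentence in two:

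1. Apply the day-28 restriction to efficacy outcomes only.
2. State that interim safety tables (deaths, all SAEs, adverse events of special interest, hospital admissions and treatment stops) cover all randomised participants with data to the cut-off, by arm, including those who die or withdraw before day 28.

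Person-days of follow-up may be shown as an additional denominator, since recent participants have had less time at risk. This is optional. If the DMC Charter describes the report contents, it should say the same.

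The cost is a sentence of SAP wording and a second denominator in the DMC tables. No new data are needed, because potential SAEs are already reported within 24 hours and safety is already collected at the weekly calls (protocol 2.8). The small downside is that some recent events will be unadjudicated when shown, and the tables can label them so.

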3 DESCRIPTIVE ANALYSES

3.1 Participant throughput

The flow of participants through the trial will be summarised using a CONSORT diagram. This will describe the numbers of participants randomised, receiving allocated treatment, withdrawing consent, and included in the ITT analysis population.

3.2 Baseline comparability of randomised groups

The following baseline characteristics will be described separately for patients randomised to tecovirimat and placebo.

- Age at randomisation
- Sex at birth
- Time since onset of skin or mucosal lesions
- Number of active lesions (1-5, 6-25, 26-100, >100)
- Number with disseminated infection (defined as >1 body region affected)
- Proportion requiring painkillers for monkeypox
- Comorbidities (diabetes, HIV, and immunosuppression related to medication or haematological disease)
- Previous orthopoxvirus vaccination

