2.8 Sample size

For the log-rank test of the primary endpoint ‘time to active lesion resolution’, the two key determinants of power are the total number of active lesion resolution events and the treatment-to-control ratio of the rate of active lesion resolution.

Table 1 displays the power of this test for various scenarios. In total, 318 patients with lesion resolution by day 28 are needed to detect a 40% improvement in the rate of lesion resolution as measured by the rate ratio (akin to a “hazard ratio” but for a positive outcome instead of death; values greater than one indicate improved outcomes) with at least 85% power and a two-sided α of 0.05. Conservatively assuming that the observed event rate of 77% from the 2007-2011 INRB/USAMRIID observational study will apply to the combined time to event data of experimental and control groups yields a total targeted sample size of 413 participants.³ A total sample size of 500 is planned to account for one interim analysis and approximately 10% losses to follow-up.

Table 1. Number of events needed to have 80% and 85% power at $2P=0.05$ to detect an improvement in the primary outcomes.

Rate Ratio	Scenario for 80% Power ($\beta=0.20$)		Scenario for 85% Power ($\beta=0.15$)	
	Number of Events Needed	Number of Patients Needed*	Number of Events Needed	Number of Patients Needed*
1.30	457	594	522	678
1.40	278	362	318	413
1.50	191	249	219	285

* Assumes that 77% of patients will experience the event and does not account for potential dropout. In the 2007-2011 INRB/USAMRIID observational study, 77% of patients reached lesion resolution (as defined above) within 22 days.

Since the event rate is uncertain, the sample size will be reviewed and revised based on blinded data (i.e. with time to event data for the experimental and control groups combined), when about 50% of the originally planned number of participants have reached determination of the primary endpoint.

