4.1 Outcomes

4.1.1 *Primary outcome*

The primary outcome is defined as the first day on which all skin lesions are scabbed or desquamated and mucosal lesions healed, up to 28 days after randomisation (regardless of whether active, unscabbed, lesions are reported on subsequent days). Missing values for a particular day will be imputed as the reported value taken nearest in time before or afterwards (counted in whole days; in the event of a tie the reported value taken beforehand will be used).

For time-to-event analyses of this outcome, the tecovirimat group will be compared with the placebo group using a stratified log-rank test (days since symptom onset ≤ 7 and >7 days). Kaplan-Meier estimates for the time to event will also be plotted, with associated log-rank p-values. The log-rank 'observed minus expected' statistic (and its variance) will also be used to estimate the average event rate ratio (and its confidence interval) for those allocated to tecovirimat vs placebo.

4.1.2 *Secondary outcomes*

Secondary outcome (i) is defined as the first day on which all skin lesions are completely resolved, meaning all scabs have dropped off with intact skin remaining underneath, and mucosal lesions have healed, up to 28 days after randomisation (regardless of whether unhealed lesions are reported on subsequent days). Imputation of missing data and the method of time-to-event analysis will be as for the primary outcome above.

The remaining secondary outcomes are defined as the time to consistently negative culture for monkeypox virus in serial self-collected swabs, either taken from the throat (secondary outcome (ii)), or the most recent active skin or mucosal lesion (secondary outcome (iii)). These swabs are collected on days 7, 14, 21, and 28 after randomisation, and will be analysed using an interval censored Weibull model. A negative culture will be considered 'consistently negative' if it is not followed by a positive culture on the same type of swab during subsequent assessments.

4.1.3 *Subsidiary outcomes*

Clinical status on an ordinal scale will be compared between tecovirimat and placebo groups using a proportional odds model.⁶ Howard's method will be used if the proportional odds assumption is not satisfied.⁷ Monkeypox virus DNA concentration will be compared between groups using the Wilcoxon rank-sum test.

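### Baseline number of active lesions is banded for the baseline table but not used in the primary log-rank test; if it is prognostic, the test may give up power that one pre-specified stratification factor would recover

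*SAP*

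**What the plan says.** SAP 2.6.1 takes as primary outcome the time to active lesion resolution, "defined as the first day on which all skin lesions are scabbed or desquamated (and mucosal lesions healed", up to day 28. SAP 4.1.1 tests it with a "stratified log-rank test (days since symptom onset ≤ 7 and >7 days", and the observed-minus-expected statistic and its variance "will also be used to estimate the average event rate ratio (and its confidence interval". Protocol 2.5.1 specifies the same test and estimate.

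SAP 3.2 opens with "The following baseline characteristics will be described separately for patients randomised to tecovirimat and placebo", and its list includes "Number of active lesions (1-5, 6-25, 26-100, >100". The count appears nowhere else:

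- **Minimisation** (protocol 2.3, SAP 2.9): the nearest factor is "Severity of rash (localised vs disseminated, defined as >1 body area affected". The primary analysis does not use that factor either.
- **Subgroups** (protocol 2.5.1, SAP 4.2): age, sex, vaccination status and time since first lesion only.
- **Baseline data** (protocol 3.3): clinical signs and symptoms are listed, but a lesion count is not named.

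SAP 2.8 sizes the trial at 318 events for a rate ratio of 1.40, "with at least 85% power and a two-sided α of 0.05".

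**The concern.** The primary event needs every active lesion to have cleared, so its time is set by the last lesion. Unless all of a participant's lesions clear on the same day, more lesions at the start should mean a later event. Lesion count is therefore a natural candidate for a strong baseline prognostic factor.

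Localised versus disseminated rash is a coarse stand-in for it. Two lesions in two regions count as disseminated, and many lesions in one region count as localised.

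When a prognostic factor is left out of a log-rank test, participants with very different chances of resolving share a risk set. The fast resolvers leave early, the mix of those still at risk drifts apart between arms, and the average rate ratio moves toward 1 relative to the ratio among participants with similar lesion counts. At stake are some points of power and the size of the reported effect. An adjustment for lesion count chosen after unblinding would have to be labelled post hoc (SAP 4.5).

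**Working it through.** **1. The plan's own figure.** Schoenfeld events = 4(z₀.₉₇₅ + z₀.₈₅)² / (ln 1.40)² = 4(1.960 + 1.036)² / 0.1132 = 317.2, so 318. Patients = 318 / 0.77 = 413. Both match SAP Table 1. After about 10% losses, 500 × 0.90 = 450 participants are evaluable, giving 450 × 0.77 = 346.5 events. At the final two-sided level of 0.0476 (Z > 1.98, SAP Table 2) the formula gives 87.5% power.

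**2. Inputs to the simulation.**
- From the documents: 1:1 allocation, 77% resolved over both arms by day 28, rate ratio 1.40 (taken here as holding within bands), whole-day times, two onset strata.
- Assumed, because the documents do not give them: band mix 35/45/17/3% or 30/40/22/8%; a constant proportional slowing per higher band; exponential times. The runs with the first mix also assume a 50/50 onset split independent of band and an onset effect of exp(0.3).

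**3. Statistics.** Z = Σ(O−E) / √ΣV and rate ratio = exp[Σ(O−E) / ΣV], summed over strata. Planned strata: onset (2). Alternative: onset × lesion band.

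**4. Planned test against onset × four bands.** N = 450, two-sided 0.0476, mix 35/45/17/3%, 10,000 trials per row, Monte Carlo SE about 0.4 points. Changes were taken before rounding.

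| Slowing per higher band | Power, planned | Power, with bands | Change | Rate ratio, planned → with bands |
|---|---|---|---|---|
| none | 87.0% | 86.1% | -0.8 | 1.42 → 1.42 |
| 15% | 86.9% | 86.5% | -0.4 | 1.41 → 1.42 |
| 30% | 83.8% | 86.4% | +2.7 | 1.40 → 1.42 |
| 40% | 80.6% | 86.4% | +5.8 | 1.38 → 1.42 |
| 50% | 76.1% | 86.4% | +10.3 | 1.35 → 1.42 |

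With no lesion effect the planned test gives 87.0%, against 87.5% by formula, so the simulation is calibrated. The estimator slightly overshoots 1.40 even then, so 1.42 is the right comparator for the last column.

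**5. Three bands (1-5, 6-25, >25), six strata.** N = 413, Z > 1.98, same mix, 3,000 trials per scenario. Power, planned / with bands:
- none: 84.6 / 83.8% (-0.8)
- 15%: 83.2 / 82.9% (-0.3)
- 30%: 80.6 / 82.9% (+2.3)
- 40%: 77.6 / 82.7% (+5.1)
- 50%: 73.2 / 83.7% (+10.5)

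Merging the top two bands loses nothing visible.

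**6. The other mix, 30/40/22/8%.** N = 413, Z > 1.98, four bands, 2,000 trials per scenario. Power goes from 79.8 to 82.8% at 30% slowing (+3.0), from 75.7 to 82.8% at 39% (+7.1), and from 68.4 to 81.9% at 50% (+13.5). At N = 450 planned power is higher, about 84% at 30% and 80% at 39%, with the same gains of about 3 and 7 points.

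**7. Validity.** With no treatment effect, the planned test's one-sided error was 2.6% and 2.4% (30% and 50% slowing, nominal 2.5%).

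**The case against.** A reader might infer that the primary test is underpowered, or its estimate biased, as the plan stands. The documents do not support that, for four reasons.

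- **Prognostic strength is unknown.** No section quantifies the effect of lesion count on time to resolution. Protocol 1.1 describes lesions as progressing uniformly, which would make stage matter more than number, and the test already stratifies on time since onset. Uniform progression describes the sequence of stages, however, not a shared finishing day. The ordinal scale in protocol 2.4.3 has a level for new lesions in the previous day, so staggered lesions are expected. The direction is plausible; the strength is open.
- **The large gains need steep gradients.** Over three steps, 30%, 40% and 50% slowing make the top band about 2.9, 4.6 and 8 times slower than the lowest (1/0.7³, 1/0.6³, 1/0.5³). A model that takes the last of many correlated lesions, set to the 9-day median in protocol 2.4.3 with assumed within-person correlation of 0.97 to 0.69, gave gains of only about -0.5 to +2 points.
- **The estimate is not biased for its own target.** SAP 4.1.1 names an average event rate ratio. The planned figure is closer to 1 only relative to a within-band ratio. If 1.40 is read as the average ratio, the stated 85% power stands and stratifying is purely a gain.
- **Chance imbalance is not a validity problem.** It is ordinary randomisation error, covered by the test and interval. SAP 3.2 would also display it.

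All four stand, and they limit the point to efficiency. They do not remove it: the possible loss from stratifying is about 1 point and the possible gain is several times that.

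**Conclusion.** The point holds as a conditional efficiency improvement. The primary analysis leaves out a baseline variable that the SAP plans to tabulate and that bears directly on the endpoint. Stratifying by lesion band changes power by about -1.4 to +0.2 points if each higher band slows resolution by 0-15%, and gains about 2-4 points at 30%, 5-8 at 40% and 9-14 at 50%. Over the same range the planned rate ratio falls from about 1.42 to between 1.33 and 1.35 at the steepest gradient.

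These figures rest on the two assumed mixes, proportional effects within bands, a within-band ratio of 1.40 and 413 to 450 evaluable participants. An even spread of 25% per band would give larger gains (up to about 21 points at 50% slowing with N = 450), but nothing in the documents suggests such a spread. The sample-size arithmetic and the type I error of the planned test are sound.

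**What to change.** Before unblinding, in SAP 4.1.1 and protocol 2.5.1:

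- Add baseline number of active lesions to the strata of the log-rank test in three bands fixed now (1-5, 6-25, >25), crossed with the existing onset factor to give six strata. Fixing the merge of the top two bands in advance avoids a data-dependent choice.
- Compute the observed-minus-expected rate ratio from the same strata.
- Apply this to the primary outcome and to complete lesion resolution, at the interim and final analyses alike. SAP 4.1.3 borrows the primary method for analgesia, so state whether the new strata apply there too.
- Keep the onset-only test as a pre-specified sensitivity analysis.
- Confirm that the count is recorded at randomisation in bands that allow this, and name it in protocol 3.3.

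If the sponsor prefers to leave the primary test alone, a pre-specified supportive analysis with these strata is the minimum.

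The cost is one SAP sentence, a matching protocol line, and roughly 1 point of power if lesion count turns out not to be prognostic. The SAP's document history places version 1.0 before both unblinded interim monitoring and unblinding of the trial statisticians; any change should carry the same status.
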